# 8.4 SIGNIFICANCE LEVEL AND POWER OF THE PRIMARY ENDPOINT AND OVERALL STATISTICAL TESTING STRATEGY

The primary endpoint analysis will be performed at the one-sided 0.025 alpha level. Any other p-values and confidence intervals will be based on a nominal two-sided 0.05 alpha level (or equivalently a one-sided 0.025 alpha level as appropriate) without adjustment for multiple comparisons.

#### 8.5 SAMPLE SIZE CALCULATION AND JUSTIFICATION

A total of 250 evaluable subjects (in a 1:1 allocation ratio) will provide 80% power assuming a population mean difference between groups of 3.2 and a common standard deviation of 9 based on a two-sided twosample t-test with an alpha of 0.05. Previous data suggests the standard deviation for 2 week improvement to be approximately 6.5; however, a conservative estimate of 9 was used for these calculations. If the observed standard deviation is less than 9, a smaller effect size will provide 80% power. In addition, this calculation is conservative since the planned test adjusting for baseline is expected to provide additional power. Sample size calculations were performed using PASS 2021 (NCSS, LLC). While some amount of missing data is expected, the primary analysis will be based on the randomized cohort of subjects and will employ multiple imputation to mitigate the impact of missing data.

The sample size for the study is practically constrained by regulatory requirements for timely submission and the impact of the COVID-19 pandemic. Accordingly, while the final formal analysis is planned for the final planned sample size, circumstances may dictate initial regulatory submission based on data available with supplemental updates provided later based on the final data set. Since the formal analysis will be based on the final planned sample size, there are no alpha implications.

# 9 DATA MANAGEMENT

#### 9.1 PROCEDURES FOR DATA MANAGEMENT

Climb will be responsible for study data management according to a project plan developed for this study in collaboration with the Sponsor and designee(s).

The details of data review and querying will be described in a Data Management Plan (DMP) that will be maintained by Climb, the Principal Investigator, and the Sponsor. This plan may be updated throughout the investigation as amended data management requirements and investigation-specific data conventions are determined.

#### 9.1.1 Electronic Patient Reported Outcomes

The Climb web-based ePRO digital health technology will be used to record and manage study data. Subjects who have been screened for study participation and signed an Informed Consent Form will selfreport their experiences during the trial using the ePRO. Subject training on ePRO usage will be conducted prior to starting study treatment with the investigational device. Investigative staff will be available to answer questions from subjects about ePRO usage and assist them with technological issues or clarifications.

Investigative staff will review all subject-entered ePRO data to monitor subject safety and identify any issues pertaining to study design or the investigational product. A subject may contact the investigative team should they wish for their reported data to be reised or corrected. An investigative team member will make the change in ePRO and enter a reason for change in ePRO as well. The ePRO includes an audit history to display changes to reported data.

Version 5.0 08-Jun-2022

# 9.1.2 Data Queries

Sponsor representatives reviewing subject ePRO data may contact the subject for clarification of data or to follow up for missing data. All changes to ePRO data will be captured in an audit trail.

## 9.1.3 Confidentiality

This clinical investigation will comply with HIPAA and any additional requirements imposed by national law concerning data protection.

A study code identification number will be used to facilitate creation of de-identified reports. Subject personal data will be processed at all times in accordance with applicable legal requirements and will be used solely for the purposes of conducting this clinical study and to aid future scientific research in the treatment of moderate to severe depressive disorder. In general, only the Sponsor or authorized designees will have direct access to subject personal data. It may also happen that representatives of national or international public health authorities (e.g., Competent Authorities) are granted direct access to subject personal data, if required by applicable law.

#### 9.2 PROCEDURES FOR VERIFICATION AND VALIDATION OF EPRO SYSTEM

The ePRO used for this trial was verified and validated by Climb's procedures for data capture validation and verification.

#### 9.3 **PROCEDURES FOR DATA RETENTION**

The Climb procedures for study data retention will be followed. All information in the ePRO will be stored in a secure validated database.

#### 9.4 SPECIFIED RETENTION PERIOD

The Sponsor shall maintain the records of the study during this investigation and for a period of 2 years after the later of the following two dates: The date on which the investigation is terminated or completed, or the date that the records are no longer required for purposes of supporting a premarket approval application, a notice of completion of a product development protocol, a humanitarian device exemption application, or a premarket notification submission.

#### 9.5 CLINICAL QUALITY ASSURANCE

The study will be conducted and monitored by the Sponsor and authorized designees. The Sponsor may appoint a Quality Assurance (QA) auditor to review the records and conduct of the study.

# **10 AMENDMENTS TO THE PROTOCOL**

Any modifications to the protocol require Sponsor approval. Once completed, the revised protocol needs to be submitted to the IRB. The protocol must receive written approval as an Amendment prior to implementing the modifications.

# **11 DEVIATIONS FROM THE PROTOCOL**

#### **11.1 INVESTIGATOR DEVIATIONS FROM PROTOCOL**

Major deviations from this protocol, except in emergency situations, require prior approval by the Sponsor. This provision does not apply to those changes made to reduce discomfort or overt risks to the subject. All major deviations and any procedures or actions taken by investigative staff must be documented in the ePRO and reported to the Sponsor within 2 days.

Minor deviations (e.g. assessment unable to be completed or outside visit window) may occur from time to time. The investigative staff should make their best effort to minimize such occurrences. Should a minor deviation occur, it should be documented in the ePRO in a timely manner.

#### 11.2 PROCEDURES FOR DEVIATION RECORDING, REPORTING AND ANALYZING

All deviations will be documented in the subject's ePRO Case Report Form and reported to the Sponsor within 2 days.

#### 11.3 CORRECTIVE AND PREVENTIVE ACTIONS AND PRINCIPAL INVESTIGATOR DISQUALIFICATION CRITERIA

Protocol deviations will be reviewed during monitoring visits. As appropriate, investigators will be required to identify corrective and preventive actions to prevent further deviations. An investigator may be disqualified from the study for repeated and/or egregious protocol deviations.

# **12 DEVICE ACCOUNTABILITY**

#### **12.1** INVESTIGATIONAL DEVICE DISPOSITION

Access to investigational devices shall be controlled by the Sponsor and authorized designee. The investigational devices shall be used only in this clinical investigation and according to the clinical trial protocol. The Sponsor shall keep records of the type and number of all investigational devices shipped to subjects including device return or disposal.

#### **12.2 CLINICAL SUPPLIES ACCOUNTABILITY**

The investigational devices provided for use in this study are intended for use only in the clinical trial outlined in this protocol and will be used only in subjects appropriately consented in this trial. The use of the supplies for other clinical or preclinical situations is strictly prohibited. The use of the investigational supplies by any third party, outside of the provisions stated in this protocol, without the express written permission of Sponsor, is strictly prohibited. The possession and use of the supplies by subjects must be closely controlled and monitored. Subjects will be required to return the used devices at the conclusion of their study participation (End of Therapy or early withdrawal/termination). All investigational supplies that are not used on a subject will be returned to the Sponsor at the end of the study.

CES-MDD	Version 5.0
FW-200-05	08-Jun-2022

The Sponsor or authorized designee shall keep records documenting the receipt, use, return and disposal of the investigational devices, which shall include:

- the date of receipt,
- identification of each investigational device (lot number/serial number or unique code),
- the expiry date, if applicable,
- the date or dates of use,
- subject identification,
- date on which the investigational device was returned/removed from subject, if applicable, and,
- the date of return to the Sponsor of unused, expired or malfunctioning investigational devices, if applicable.

# 12.3 INVESTIGATIONAL DEVICE ACCOUNTABILITY RECORD

Investigational devices will be shipped directly to subjects by the Sponsor's authorized blinded designee. Upon receipt of the investigational device, the subject will record confirmation of receipt in ePRO. The Sponsor's authorized designee will review ePRO device accountability data in a timely manner to ensure accurate record keeping of final disposition of all investigational materials. Device accountability data in ePRO will be reconciled with the Sponsor's investigational device shipping and return records during the trial.

# **13 REGULATORY COMPLIANCE**

# **13.1 STATEMENTS OF COMPLIANCE**

- This clinical investigation will be conducted in compliance with the principles that have their origin in the latest version of the Declaration of Helsinki, October 2013.
- This clinical investigation will comply with 21 CFR Parts 11, 50, 54, 56, and 812 requirements of FDA, the requirements of the IRB, ISO 14155:2020, and other applicable regional or national regulations, whichever provides the greater protection of the individual.
- This clinical investigation will not begin until required approval(s)/favorable opinion(s) have been obtained from the applicable IRB or regulatory authority.
- Any additional requirements imposed by an IRB or regulatory authority will be followed in the conduct of this clinical trial.
- The Sponsor has obtained clinical trial insurance that will cover expenses in the event of any physical injury resulting from research procedures.

#### **13.2 INSTITUTIONAL REVIEW BOARD**

Prior to the initiation of this clinical investigation, on behalf of the Principal Investigator, Climb will submit the protocol, patient-facing materials, informed consent form template, and any other required documents to the IRB for review and approval. The Principal Investigator, and any other member of the investigative team, if a member of the IRB, must not participate in the decision-making. A list of the members of the IRB reviewing this protocol will be requested.

A signed and dated letter from the IRB granting approval/favorable opinion must be received prior to the initiation of the clinical investigation.

#### **13.3 PROVISION OF INVESTIGATIONAL DEVICE**

Investigational products will not be shipped to the first enrolled subject until investigative staff responsible for conducting device training with subjects have themselves completed the required training on device usage/handling and this clinical study protocol.

#### 13.4 PRINCIPAL INVESTIGATOR'S STUDY REPORTING RESPONSIBILITIES

The Investigator agrees to the following reporting responsibilities:

- Collaborate with the Sponsor, NAMSA, and Climb to provide the required reports to the IRB for the duration of the study. Copies of IRB correspondence must be provided to the Sponsor for Trial Master File filing.
- Collaborate with Climb and NAMSA to submit the Investigator's Final Report to the IRB per the IRB's requirements after the study's completion or termination.
- Collaborate with the Sponsor, Climb, NAMSA, and investigative staff to receive any pertinent details that may impact the conduct of the clinical study and require IRB reporting per IRB policy.

# **14 INFORMED CONSENT PROCESS**

#### 14.1 GENERAL INFORMED CONSENT PROCESS

The Sponsor will provide a template informed consent form (ICF) for IRB review/approval.

The Principal Investigator or investigative staff designee must administer this approved ICF to each prospective study subject, and obtain the subject's signature along with the date of consent prior to enrollment in the study. The ICF for this study will be electronic and signatures will be obtained via DocuSign or a similar platform. The ICF must be obtained in accordance with the applicable guidelines of the Declaration of Helsinki, or local regulations and laws, whichever represents the greater protection of the individual. Subjects must be informed about their right to withdraw from the study at any time and for any reason without sanction, penalty, or loss of benefits to which the subject is otherwise entitled and also be informed that withdrawal from the study will not jeopardize their future medical care. A

copy of their signed ICF must be given electronically to each subject enrolled in the study. This will be provided electronically for their records. The institutional standard subject consent form does not replace the study ICF.

# 15 ADVERSE EVENTS, ADVERSE DEVICE EFFECTS AND DEVICE DEFICIENCIES

In this trial, all adverse events (AEs) and device deficiencies that occur will be reported by the subject using ePRO and reviewed by the Sponsor (or designee) and Principal Investigator in a timely manner. All AEs will be followed by the Sponsor and Principal Investigator or designee until the last event has resolved, the condition has stabilized, or the subject exits the trial, whichever comes last. All follow up reports for AEs will be documented in detail in the ePRO.

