# 7.3.15.3 LOST TO FOLLOW-UP

The effort to obtain follow-up information should include 3 attempts to make contact with the subject via telephone or text. All contact efforts to obtain follow-up information should be documented in ePRO.

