#### **15.1 DEFINITIONS**

Adverse Event (AE): Any untoward medical occurrence, unintended disease or injury, or untoward clinical signs (including abnormal laboratory findings) in subjects, users, or other persons, whether or not related to the investigational medical device and whether anticipated or unanticipated.

- 1. This definition includes events related to the investigational medical device.
- 2. This definition includes events related to the procedures involved.
- 3. For users or other persons, this definition is restricted to events related to investigational medical devices.

Adverse Device Effect (ADE): Adverse Event related to the use of an investigational medical device.

1. This definition includes adverse events resulting from insufficient or inadequate instructions for use, deployment, implantation, installation, or operation, or any malfunction of the investigational medical device.

2. This definition includes any event resulting from use error or from intentional misuse of the investigational medical device.

**Device Deficiency:** Inadequacy of a medical device with respect to its identity, quality, durability, reliability, usability, safety, or performance. Device deficiencies include malfunctions, use errors, and inadequacy in the information supplied by the manufacturer including labeling.

Serious Adverse Device Effect (SADE): Adverse Device Effect that has resulted in any of the consequences characteristic of a serious adverse event.

Serious Adverse Event (SAE): Adverse Event that led to any of the following:

- (a) death;
- (b) serious deterioration in the health of the subject, that resulted in any of the following:
  - i. a life-threatening illness or injury, or
  - ii. permanent impairment of a body structure or a body function including chronic diseases, or iii. inpatient or prolonged hospitalization, or

iv. medical or surgical intervention to prevent life-threatening illness or injury, or permanent impairment to a body structure or a body function,

(c) fetal distress, fetal death or a congenital physical or mental impairment or birth defect.

NOTE: Planned hospitalization for a pre-existing condition, without serious deterioration in health, is not considered a serious adverse event.

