# **15.2 REPORTING**

#### **15.2.1 Investigator Responsibilities**

All Serious Adverse Events (SAEs), Serious Adverse Device Effects (SADEs, both Anticipated or Unanticipated), including any Device Deficiency that could have led to an SADE, must be reported to the Sponsor or designee within 24 hours of knowledge of the event. It is the responsibility of the Sponsor or designee to report the occurrence of any SAE, SADE, and/or UADE to the IRB according to IRB guidelines and national laws and regulations.

The Principal Investigator or designee will contact all subjects who record an adverse event or potential adverse event in ePRO. The subject will be asked to provide the following for the event:

- Any further details about the event or the subject's experience using the investigational product not already recorded in ePRO, if deemed necessary by the investigator Outcome, with options to include:
  - Ongoing/Not Resolved/Not Recovered
  - Recovering/Resolving
  - O Recovered/Resolved

- Recovered/Resolved with Sequelae
- Unknown
- Resolution date if the outcome is reported as recovered/resolved, with or without sequelae 

   Any treatments taken for the event and/or any actions taken to receive or schedule treatment
   Action taken with the study treatment in response to the event, with options including: 

   No action
  - Discontinuation of study treatment
  - Temporary halt of the study treatment; if temporary halt, the subject will be asked if the event resolved or continued after stopping the study treatment and the dates when treatment was paused.
- Relationship of the event to the use of the investigational device, reported as either Related or Not related

The investigator will review all of the reported information from the subject and separately record their causality using the following options:

- Not Related: An AE which cannot be attributed to the study device.
- Unknown Relationship: The relationship of the AE to the device cannot be determined.
- Possible: The AE occurs within a reasonable time sequence to study device usage and there is some evidence to "possibly" suggest a causal relationship. However, the influence of other factors such as underlying disease, concomitant medications, or concurrent treatment may have contributed to the event.
- Probable: The temporal sequence between the device use and the event is such that the relationship is likely or subject's condition or concomitant therapy could have caused the AE.

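### Adverse-event intake and loss-to-follow-up tracing both run through the subject, so a death or continuing hospital admission in a subject who stays silent can be recorded as loss to follow-up

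*Combined protocol and SAP*

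**What the plan says.** **Intake.** Section 15 says that "all adverse events (AEs) and device deficiencies that occur will be reported by the subject using ePRO", with review by the Sponsor and the Principal Investigator.

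**Event details.** Section 15.2.1 starts from the subject's entry: "The Principal Investigator or designee will contact all subjects who record an adverse event or potential adverse event in ePRO". It continues: "The subject will be asked to provide the following for the event". The outcomes listed are ongoing, recovering, recovered, "Recovered/Resolved with Sequelae" and unknown. The investigator separately records causality and whether the event is serious.

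**Seriousness.** Section 15.1 puts death first among the SAE criteria and also includes "inpatient or prolonged hospitalization".

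**Reporting clock.** Under Section 15.2.1, SAEs "must be reported to the Sponsor or designee within 24 hours of knowledge of the event".

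**Silent subjects.** Section 7.3.15.3 says: "The effort to obtain follow-up information should include 3 attempts to make contact with the subject via telephone or text".

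**Withdrawal.** Section 7.3.15.1 lists death and loss to follow-up as separate reasons and requires staff to contact subjects who discontinue, for safety. At early withdrawal, Section 7.3.14 has staff ask the subject to enter the adverse event in ePRO.

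**The concern.** Death and a long admission are the events that a subject is least able to log. The trial has no clinic visits, so staff do not meet subjects or their families. Version 5.0 widened the population to severe depression, with BDI-II scores up to 63, and Section 16 treats subjects with MDD as vulnerable. Safety is half of the objective in Section 6.2.

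If a silent subject who died or is still in hospital looks the same in the data as one who lost interest, a report of no SAEs says nothing about the subjects coded as lost. An imbalance between arms among those subjects would also go unseen.

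**Working it through.** The plan gives no figure on this point, so the check is mainly of the text.

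**Step 1: follow three cases through the written process.**

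| Case | Route in the text | Result |
|---|---|---|
| Subject admitted, then resumes ePRO | Daily health-status question (7.3.8, 7.3.10, 7.3.12); AE questions at Weeks 1, 2 and 4 (7.3.9, 7.3.11, 7.3.13) | Admission can be reported late |
| Death that staff happen to hear of | 24-hour duty (15.2.1); death as withdrawal reason (7.3.15.1) | Can be recorded and reported, but no fatal AE outcome is listed |
| Death or continuing admission, subject silent, nobody contacts staff | At least three calls or texts to the subject (7.3.15.3) | Staff do not learn of it; lost to follow-up is the reason that remains |

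**Step 2: look for another source in the third case.**
- Section 7.3.15.1 requires a safety contact, directed to the subject.
- Section 9.1.1 has staff review what the subject has entered.
- Section 9.1.2 lets Sponsor representatives ask the subject about missing data.
- Section 7.3.6 has a log of subjects' contact information; its fields are not described.
- Section 7.4.1 allows staff-entered data and medical records kept by staff as source, but does not say how staff would obtain outside information.

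Each contact goes to the subject or depends on the subject's own entries. The visible text names no next of kin, alternate contact, treating clinician, hospital record or vital-status search.

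**Step 3: compare the SAE definition with the outcome list.** Section 15.1 makes death an SAE. Section 15.2.1 lists five outcomes, none fatal, and describes no separate outcome field for the investigator to complete.

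**Step 4: context from the earlier remote trial (Section 4.2).** Completers of the 4-week assessment: 83 + 78 = 161 of 275. Without it: 275 − 161 = 114, and 114/275 = 41%. By arm this is 54/137 = 39% and 60/138 = 43%. Week 4 side-effect answers in Table 1 come from 110 of 275 (40%). These are missing assessments. They do not show that SAE status was unknown, because Section 4.2 says that side effects were assessed throughout that study, including at Week 2.

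**Step 5: what a zero SAE count would mean (illustration only).** The unknown shares below are assumptions; the plan gives no attrition rate. With no SAE among *n* known subjects, the one-sided 95% upper bound on risk is 1 − 0.05^(1/*n*).

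| Status unknown, of 250 | Known *n* | Upper bound | Possible SAEs among unknown |
|---|---|---|---|
| 0 | 250 | 1.2% | 0 |
| 25 (10%) | 225 | 1.3% | 0 to 25 |
| 50 (20%) | 200 | 1.5% | 0 to 50 |
| 75 (30%) | 175 | 1.7% | 0 to 75 |

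The bound changes little, but it carries over to the whole cohort only if silent subjects have the same risk as the rest. That is the assumption in doubt here, and without it the last column is all that can be said.

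**The case against.** A reader might infer that adverse events can enter the trial only through the subject, that a death would necessarily be filed as loss to follow-up, or that three attempts is the limit. The documents do not support any of these:
- The 24-hour duty applies to any SAE that staff know of, whatever the source, and staff-entered data count as source data.
- Death has its own withdrawal reason, so a known death need not be coded as lost.
- Three attempts is a minimum, and there is a further duty to contact subjects who discontinue.
- Daily and weekly prompts give a returning subject several chances to report an admission.

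The outcome list is also introduced as options put to a living subject and is not stated to be exhaustive, so the missing fatal code may be a drafting gap. Section 15.4, titled Emergency Contact Details in the contents list, and the consent pages were removed and could bear on an alternate contact. Finally, the safety endpoint in Section 6.4 counts device- and procedure-related events, so an unrelated admission would not enter it.

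These points narrow the gap to subjects who stay silent, but they do not close it. A duty that starts at knowledge does not provide the knowledge, and more attempts to reach the same person do not help if that person has died. An event that nobody learns of cannot be judged unrelated either.

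**Conclusion.** The concern holds in this limited form and should be acted on. Followed as written, the visible text gives staff no route to learn of a death or continuing admission in a subject who stays silent, and such an SAE can be recorded as loss to follow-up. The missing fatal outcome is a smaller, separate inconsistency with Section 15.1.

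The number of missed SAEs cannot be estimated: the documents give neither an SAE risk nor the share of events that subjects would fail to log. A reader might take the 41% from the earlier trial as the share whose SAE status would be unknown here. It counts missing Week 4 assessments and does not support that reading. The point concerns safety ascertainment and makes no claim about the primary efficacy analysis. It rests on the supplied text and would weaken if Section 15.4 or the consent form already provides for an alternate contact.

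**What to change.** 1. **Section 15:** state that adverse events may be reported by the subject, by an alternate contact named at consent, or entered by investigative staff who learn of them from any source, with the source recorded.
2. **Section 15.2.1:** add a fatal category to the AE outcome options.
3. **Section 7.3.15.3:** before a subject is coded as lost to follow-up, require one documented call to the alternate contact to establish vital and hospitalisation status.
4. **Safety reporting:** show status known or unknown by arm beside the SAE table.

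The cost is one alternate-contact field, one line in the consent form with the IRB amendment it needs, one outcome code, and a few calls by existing staff. The downside is one extra item of personal data per subject. If the removed text already provides for such a contact, only the cross-references, the outcome code and the status table are needed.
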